## Early Global Development in Tuberous Sclerosis

In addition, for the cognitive outcomes, using a t-test on the final Bayley-III Cognitive Scores shows that when the sample size is 24 participants per arm there is 85% power to detect an effect size on the cognitive component of the Bayley III of 0.885 when the Type I error is 0.05, two tailed. The plausibility of achieving this effect size was assessed using published data from the Bayley III manual. In children with Pervasive Developmental Disorders, the average cognitive score is 5.7 (sd 2.9) compared to matched controls with a mean of 11.0 (sd 3.0). The effect size for the difference between this disorder and the matched controls is 1.77  $[(11.0-5.7)/3.0]$ , a difference double the effect size detectable with the sample size available for this Phase IIb trial. While it is unlikely that early treatment would return these patients to normal levels, we are hypothesizing as the alternative that we will achieve an effect size of approximately 50% of the difference compared to normal scores. That is, we will use a sample size necessary to detect an effect size of 0.885.

To further examine the ability of the sample size to achieve the goals of the study, we first examined the sensitivity of the design to our assumption of the standard deviation by examining the standard deviation against other groups of special interest.

The Bayley-III cognitive test battery shows that the standard deviations vary from a low of 1.9 at an assessment in Downs Syndrome Children to 3.5 amongst SGA infants. The table below shows the standard deviations for various special groups.

PDD	CP	DD	Language impaired	Perf At Risk	Asphyx	Fetal Alcohol	SGA	Premie
2.9	3.1	1.9	2.4	3.2	3.1	2.7	3.5	3.1

The average standard deviation is 2.9, the median is 3.1, so again, using 3.0 in our calculations seemed reasonable.

We next estimated the sensitivity of the trial in terms of the power for testing the time-averaged difference (TAD) between two means in a *repeated measures* design. In the TAD model, we assumed the mean difference starts to become evident at 3 months and is continuing or enlarging at 12, 24 and 36 months. The correlation amongst Bayley-III Cognitive assessments within person was varied from 0.10 to 0.80.

The power for this study is actually slightly higher than 85% because the analysis approach planned will make use of repeated measures analyses enabling more information to be gleaned from the data. Information and thus power is gained because partial data are used from the annual cognitive assessment measurement on those completing the trial. Thus, the sample size provides further protection against minor deviations from the assumptions used to calculate the feasibility based on the sample size.

### **BOSA PRELIMINARY DATA Based on the ADOS (Reference BOSA Manual version 6-25-20)**

As of 7/1/2020 no BOSA data has yet been collected or analyzed. Preliminary data analyses were conducted by MAKING BETTER MEASURES Group at UCLA led by [name].

They used binary ADOS algorithm codes scored from full standardized ADOS administrations. Based on the findings with the ADOS, it was determined that a cut-off estimate of 5 for Modules T,1 and 2 yielded the best pairing of sensitivity and specificity. It is important to note that these cut-offs are only estimates and were determined using ADOS data (not BOSA data). They may also not reflect scores from much briefer and less nuanced BOSA administration. Thus the information should only be used to inform clinical decisions when using the BOSA in combination with other sources of information. These estimates are intended to give the physicians a sense of what may come and may change as data is collected on BOSA administration.

Given the age of the participants, the PREVeNT study will be using two BOSA versions:

- 1) BOSA-MV which is appropriate for individuals of any age who are minimally verbal (i.e., nonverbal or use only single words/rote phrases) and includes sets of free play toys and bubbles.
- 2) BOSA-PSYF which is appropriate for individuals of any age who use flexible phrase speech or verbally fluent children under the age of 6-8 and includes sets of free play toys, a dollhouse with figurines and bubbles.

The sensitivities at a cut-off of 4 or 5 ranged from 0.80 to 0.93 (Module T: 0.84, Module 1: 0.93, Module 2: 0.86, Module 3: 0.84, Module 4: 0.80). Thus, clinicians should take note that similar to the ADOS-2, there will be individuals who have autism who will have scores lower than the cut-offs, particularly those who do not display repetitive behaviors during the BOSA. For this reason, it is very important to supplement the BOSA with the ADI-R caregiver interview.

The specificity at a cut-off of 4 or 5 also ranged widely (Module T: 0.76, Module1: 0.84, Module 2: 0.80, Module 3: 0.76, Module 4: 0.65), though the AUC's consistently exceeded 0.80. These low specificities mean that false positives will be common when comparing the BOSA scores to these estimated cut-offs and should be cross checked with other sources of information.

## **Analyses**

The primary analyses for this Phase IIb trial consists of two testing hypotheses: time to onset of a first clinical seizure, documenting that the intervening variable (i.e. vigabatrin treatment) does indeed reduce or delay clinical seizures and comparison of the developmental outcomes at 24 months. While vigabatrin is used to control seizures and thus suppress them once seizure onset has been identified, it is presumed that if given prior to occurrence of clinical seizures occurring such a delay will be observed, but this is untested. Thus, the study endpoint of time to first clinical seizure is an essential step in determining the impact on developmental ability. The first step in the analyses will include demonstrating a difference between the proportion seizure free in the treatment arm versus placebo. This will be assessed at two years of follow-up using a chi square test and an intention to treat analysis. Supportive analyses will use a time to first seizure analysis using Cox regression methods to evaluate the treatment effects. Kaplan Meier analyses will provide graphical and overall test of the incidence of seizures. Cox models with age, gender, baseline number of epileptiform discharges included with treatment group will be attempted keeping in mind the relatively small sample size. Tests will use 2 sided Type I errors of 0.05.

The next key analysis to move to a go decision for Phase III will focus on the Bayley-III. While ideally the primary assessment would be made at age 5 or 6, there will be insufficient follow-up to make such an assessment in this grant period. We will perform assessment of the Bayley-III using the standardized cognitive scores over time using the constrained longitudinal data analysis (cLDA) method proposed by Liang and Zeger

which assumes a common mean across treatment groups at Baseline and a different mean for each treatment at each of the post-Baseline time points (12, 24, and 36 months for those who have them). In this model, we use a response vector that includes the time 0 or the baseline measure and assessments at each post-baseline observation time point. Each time point is considered a categorical variable so that no overall linear restrictions are imposed on the means over time.

The unanticipated pandemic which has interrupted almost all studies has caused us to develop an alternative assessment during the pandemic for safety of the participants as well as providing some information on our primary endpoint if a key time point visit occurs during this time period. Conversion to approximate ADOS-2 scores will be attempted using internal and data external to PREVeNT. If such linkage is not adequate for mapping between the two methods of assessment, imputation will be done using this information as a covariate to aid in the imputation. Since it is unknown at this time, how many visits will be impacted by this study interruptions, a formal plan has not been put into place. If an exam is not one of the endpoint exams, the impact will be far less than if it is a final visit for the participant. This will be assessed and the final plan decided before breaking the blind. Before the final analysis begins, we will contact Making Better Measures and [name] regarding additional data on the BOSA measure for accessing autism.

Additional analyses will focus assessing whether the treatment effect is symptomatic or potentially a disease modifying effect assessed by a comparison of the early differences (12 months minus baseline) compared to late differences (24 month minus 12 month or 36 minus 12). Corresponding 95% confidence intervals (CIs), and nominal (unadjusted) P-values will be estimated using the cLDA model. If the contrast between the early and late differences is significant, this is consistent with a disease modifying effect.

A second consideration is the observation time during the trial. Since the patients will be put on active therapy following an event, a second consideration is the duration of seizure suppression, that is, the time after an event has occurred up until two years. This is effectively, the medication possession ratio ( $MPR = \text{total time on vigabatrin treatment} / \text{total follow-up time}$ ). We expect the delayed treatment group on average to have Vigabatrin treatment for slightly less than 1-2 years and effectively 2-3 years for early treatment group. This is based on assuming a uniform distribution of occurrence of the clinical seizures. Clearly, if there were no significant differences between the early and late treatment in this parameter, we would expect a negative outcome. However, this parameter may be useful in understanding the extent of the differences observed. The MPR, if there is a relationship to the primary outcome, may be useful for imputation of missing data (which we expect to be quite low). This variable can be entered into the cLDA model and assessed using the procedures of MacKinnon for testing mediation. The mediation model would say that the effect of the treatment on the outcome of the cognitive scores is mediated through the MPR and not the earlier intervention. The sample size may not allow a clear answer to this question, but if earlier intervention before the onset of a clinical seizure is key in preservation of cognitive function, then the mediation will not be demonstrated.

Drug resistant epilepsy: For the current study, drug resistant epilepsy is defined as the “failure of adequate trials of two tolerated appropriately chosen and used antiepileptic drug schedules (whether as monotherapy or in combination) to achieve sustained seizure freedom as put forth by the International League Against Epilepsy. This will be compared between the early and delayed treatment groups using Fisher’s exact test.

Additional developmental measures and ASD Risk: The sub-scores on the Bayley-III and the composite score estimated using Hotelling’s  $T^2$ . The power for this endpoint will vary, but is expected to be similar to the primary. In the children with Pervasive Developmental Disorders, the effect sizes versus normal matched controls were 1.77, 1.67, 1.17 and 1.33 for the Receptive communication, Expressive Communication, Fine and gross motor sub-scores respectively. The ADOS2 will be completed at 24 and 36 months of age as a neurodevelopmental assessment for symptoms of ASD. The results from Study Arm A (seizure free, no treatment), Arm B (VGB versus. Placebo), and subjects with electrographic seizures at baseline EEG who move directly into Open Label treatment will be compared increasing our power to assess differences (Figure1).

Determination of vigabatrin safety as a preventative treatment for clinical seizures in infants with TSC will be assessed using comparison between the treatment groups and as a summary of exposure time on the drug. The outcome measure will be percentage of patients in each group (vigabatrin early treatment vs. vigabatrin delayed treatment) with treatment associated adverse events (AEs), serious adverse events (SAEs), and risk evaluation and mitigation strategy (REMS) measures. Treatment related AEs and SAEs will be monitored and tabulated. Given the expectation that the delayed group will cross-over to active treatment sooner than the early treatment group, adverse events will be characterized using life table approaches to ensure adjustment for exposure time. Thus, counts of individuals with AEs, total number of specific AEs and rate per months of follow-up will all be provided and assessed for any differences and for the safety population (early plus late on person years of exposure basis). Events of specific interest and risk evaluation and mitigation strategy (REMS) measures will be compared, including any and all ophthalmologic problems that may arise. Data from the negative control group (estimated to be approximately 15-20 patients) will also be used to compare the occurrence of AEs and SAEs.

EEG biomarker feasibility: The outcome measure will be the sensitivity and specificity of EEG epileptiform activity in predicting outcomes at 24 months for each treatment group. To confirm the feasibility of using EEG biomarkers to identify TSC infants at risk for developing epilepsy, sensitivity and specificity of EEG epileptiform activity at each time-point for predicting subsequent development of epilepsy by 24 months of age will be conducted within each treatment arm. Successful treatment in the vigabatrin arm should produce significantly poorer specificity and lower positive predictive value (PPV) by mitigating the predictive power of the EEG epileptiform activity. Exploratory analysis will further evaluate the timing of EEG change with time to seizure onset and type of EEG change with epilepsy type and treatment response as a covariate in the Cox proportional hazards assessment of time to clinical seizure. Additional analysis will evaluate the separate impact of TSC clinical features and concurrent AEDs. Our estimate is that 75% will develop the EEG biomarker prior to clinical seizures, some of the enrolled infants will

develop neither EEG biomarker nor seizures and some will develop seizures prior to being identified with the EEG biomarker or never develop the EEG biomarker despite the onset of clinical seizures. If the incidence of developing the EEG biomarker relative to the incidence of seizures without the EEG biomarker is very low, then the efficacy of treatment would have to be great to warrant the cost of monitoring. Thus, evaluation of this aim will be a tradeoff between biomarker incidences versus the treatment benefit. Descriptive statistics and numbers needed to treat (NNT) will be used to evaluate this endpoint.

Additional measures and analyses considerations: We will use descriptive statistics to quantify the percentage of patients requiring unblinded treatment after randomization and the duration of blinded treatment within the study period. We will also determine the percentage of randomized patients at 24 and 36 months of age with drug-resistant epilepsy as a clinically meaningful and significant correlate to the time to first seizure measure. As noted above, Cox regression models will be attempted with the pre-treatment covariates from the baseline and index EEG (that is, the biomarker findings that initiated the randomization) to examine if there are gradients in the predictors and levels of risk/time to events that can be predicted. These analyses will be done both within the treatment group and with the interaction of treatment and biomarkers included in the model. Since subject randomization is based on EEG findings, not seizure onset and the most common age of seizure onset is 3-7 months based on published natural history studies and the data from our P20-NS080199 study. The subjects will be stratified into two groups for the analysis: 1) subjects randomized based on EEG biomarkers <12months, 2) subjects randomized based on EEG biomarker >12 months of age. There will be 2 additional groups in the analysis: subjects with normal EEGs, seizure free and never randomized and subjects with electrographic seizures at baseline, never randomized but treated with vigabatrin (the 28-30 children not randomized). Additional analysis will be done to measure the impact of concomitant AEDs used during the study.

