### **Secondary Study Objectives:**

- 1) Determine the effectiveness of early versus delayed treatment with vigabatrin in clinical seizure prevention. The outcome measure will be time to first clinical seizure following randomization. The prevalence of drug-resistant epilepsy will be assessed at 24 months for each group (vigabatrin early treatment vs. vigabatrin delayed treatment).
- 2) Determine the impact of early versus late treatment on the other components of the Bayley-III (receptive communication, expressive communication, fine and gross motor skills) and risk of autism spectrum disorders (ASD). The primary outcome measures for this objective will be subdomain scores of the Bayley-III, Vineland-II (Survey Interview Form), Beery Visual Motor Integration (VMI), and ADOS2 at 24 months. Additional exploratory analysis will be completed at 36 months to assess changes observed at 24 months are consistent with those seen at 36 months and indicative of long-term outcome. At 36 months of age subjects will also complete the Peabody Picture Vocabulary Test (PPVT). During the COVID-19 Pandemic in order to minimize the risk of infection to observer and infant until the completion of the study the Brief Observation of Symptoms of Autism (BOSA) will be administered at 24- and 36-month visits. Additionally, the ADI-R will be administered at the 36-month visit.
- 3) Confirm vigabatrin safety as a preventative treatment for clinical seizures in infants with TSC. The outcome measure will be percentage of patients in each group (vigabatrin early treatment vs. vigabatrin delayed treatment) with treatment associated adverse events (AEs), serious adverse events (SAEs), and risk evaluation and mitigation strategy (REMS) measures.
- 4) Confirm of the feasibility of using EEG biomarkers to identify TSC infants at risk for developing epilepsy. The outcome measure will be the sensitivity and specificity of EEG epileptiform activity in predicting epilepsy outcomes at 24 months within treatment groups.

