To further maintain the treatment blind, subjects who experience their first seizure after randomization to either vigabatrin or placebo will follow the same blinded 2 week transition to open label vigabatrin (dose increased to 150mg/kg/day in the open label phase), so that all patients regardless of randomization group will exit the blinded treatment phase in identical fashion. This way, neither the treating physician nor the parent/guardian would know which treatment group the child had been assigned. Only the PREVeNT trial independent medical monitor and research pharmacists at each site would have access to randomization assignments throughout the study. The blinded 2 week transition phase will also occur if the subjects in Arm A are seizure free at the time of their 24 month of age study visit. They will be tapered off the study drug (vigabatrin or placebo) without breaking the treatment blind and continue to be followed for the duration of the study (36 months) under best medical care (*i.e.* if seizures develop, vigabatrin may be initiated).

Both vigabatrin and placebo will be repackaged into identical aluminum foil sachets so as to maintain treatment blinding and distribute as appropriate to the investigational pharmacies at local participating sites for individual patient distribution and administration. For administration, the entire content of one sachet (500 mg active drug) is dissolved in 10 ml water for oral administration that is dosed according to body weight 50-150 mg/kg/day divided BID. Dosing will follow established recommended guidelines (50 mg/kg/day and increased as needed by 50 mg/kg/day every 3 days up to 100mg/kg/day during the blinded phase of the study, divided BID).

Only those subjects who have clinical seizures or electrographic seizures in the blinded treatment phase of the study will transition to open label vigabatrin to a dose of 150mg/kg/day.

Note\*\* Subjects who have consented and at the time of their baseline study visit and show evidence of electrographic and/or clinical seizure(s) on their initial video EEG will exit from the PREVeNT study and proceed with initiation of management of their clinical condition.

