All patients on placebo or vigabatrin will exit the blinded treatment phase (TREATMENT ARM A) at the onset of electrographic and/or clinical seizures or 24 months of age whichever comes first. Subjects experiencing clinical seizures will undergo a 2 week blinded transition to open label vigabatrin to a target dose of 150mg/kg/day, thus maintaining the blind. The treating clinician at that time may further optimize treatment with vigabatrin as tolerated, add adjunctive treatment, or transition to alternative AED according to best clinical judgment and established standard of care. All seizure treatments and dosing will be recorded and analyzed for synergistic effects, efficacy for specific seizure types, impact on long-term epilepsy and developmental outcome measures, and safety. Vigabatrin safety data will include the ophthalmologic examination data elements as outlined in the protocol and any potentially vigabatrin related changes

noted on routine clinical brain MRI that are obtained as part of clinical care during the subjects PREVeNT participation.

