If electrographic or clinical seizures occur while on study drug, they will transition into the Open label phase of the study (Arm B) and continue to be followed until 36 months of age as per the PREVeNT protocol schedule. If the seizures are not controlled in the Open label phase at the vigabatrin maximum dose of 150mg/kg/day, the investigator may change the antiepileptic medication as clinically warranted to improve seizure control (including tapering off vigabatrin). These subjects will remain in the open arm of the study for the duration of the protocol (36 months).

Based on the TSC-EBS data, it is estimated that 30% of subjects (24 subjects) in Arm C will not be treated but continue in the study until the age of 36 months (Table 2).

See Pharmacy Manual for details of packaging and labeling, product tracking and accountability, and product disposal and destruction.

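### The named seizure endpoint is the first clinical seizure, but an electrographic seizure alone also starts open-label vigabatrin, and the plan does not say how a child switched that way is counted

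*Combined protocol and SAP*

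**What the plan says.** **Endpoint.** Secondary objective 1 reads: "The outcome measure will be time to first clinical seizure following randomization". The Analyses section makes "time to onset of a first clinical seizure" one of its two primary hypotheses, and the EEG biomarker paragraph again refers to time to clinical seizure.

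**Tests.** The first step is "demonstrating a difference between the proportion seizure free in the treatment arm versus placebo". The method follows: "This will be assessed at two years of follow-up using a chi square test and an intention to treat analysis". The supportive Cox and Kaplan-Meier analyses are described by first seizure and by seizure incidence. None of these three descriptions says which seizure type counts.

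**Trigger for open-label drug.** In the protocol description, after the exclusion criteria, randomised children "will exit the blinded treatment phase (TREATMENT ARM A) at the onset of electrographic and/or clinical seizures", or at 24 months of age if that comes first. The same part states: "Only those subjects who have clinical seizures or electrographic seizures in the blinded treatment phase of the study will transition to open label vigabatrin". The Vigabatrin and Placebo section agrees: "If electrographic or clinical seizures occur while on study drug, they will transition into the Open label phase of the study (Arm B".

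**Detection.** Video-EEGs of one hour are scheduled every 6 weeks to 12 months of age and every 3 months to 24 months. During the blinded phase the site reads each EEG. If it shows seizures, the trial's central reader is asked to confirm, and the central reading decides whether the child moves to open label.

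**The concern.** The event in the named endpoint and the event that ends blinded treatment are different. A placebo child with an electrographic seizure at a scheduled EEG starts active drug with no clinical seizure recorded. If that child then stays free of clinical seizures, a clinical-only count credits the open-label benefit to placebo. Censoring at the switch is no remedy. The child has just had a seizure, so the censoring is informative.

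The discussion of the medication possession ratio in the Analyses section reasons as if active therapy always comes after the event. That does not hold for a child switched on an electrographic seizure if the event is clinical.

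At stake is the test of mechanism, on which the plan rests its reading of the Bayley-III result.

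**Working it through.** **1. Inputs from the plan** (sample-size text under the Primary Study Objective heading of the statistical section): 24 per arm; placebo seizure rate 22/24 = 0.917; vigabatrin rate 5/24 = 0.208; fallback vigabatrin rate 10/24 = 0.417; Fisher's exact test, two-sided 0.05; stated power 99%, and above 90% at the fallback.

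**2. Reproducing the plan.** Enumerating both binomials with two-sided Fisher p ≤ 0.05 gives 99.98% for 0.917 versus 0.208 and 96.3% for 0.917 versus 0.417. Both stated figures hold.

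**3. Inputs not in the documents.** Let e be the share of children with a seizure whose first seizure is electrographic only. Let q be the proportion of their later clinical seizures that the switch prevents by 24 months. Neither is given. I take e = 10%, 20% and 30%. For q I use two values tied to the plan's own rates: 19/24 = 0.79 (the planned vigabatrin result) and 1 − 0.417 = 0.583 (the fallback result).

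**4. Formula under clinical-only counting.** Placebo rate = 0.917 × (1 − e·q). The vigabatrin rate is multiplied by the same factor if both arms are diluted, and is unchanged if only placebo is. For example, with e = 0.30 and q = 0.583 the factor is 1 − 0.175 = 0.825. Placebo becomes 0.757 and a vigabatrin rate of 0.417 becomes 0.344.

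**5. Exact Fisher power, 24 per arm:**

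| Vigabatrin rate | q | Diluted | e = 10% | e = 20% | e = 30% |
|---|---|---|---|---|---|
| 0.208 | 0.79 | both arms | 99.8% | 99.0% | 96.9% |
| 0.208 | 0.79 | placebo only | 99.7% | 97.9% | 92.1% |
| 0.417 | 0.583 | both arms | 91% | 85% | 78% |
| 0.417 | 0.583 | placebo only | 88% | 75% | 59% |
| 0.417 | 0.79 | both arms | 89% | 80% | 70% |
| 0.417 | 0.79 | placebo only | 84% | 64% | 42% |

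The last two rows combine a poor blinded result with a good open-label one, so the 0.583 rows are the more coherent fallback. The planned chi-square test without continuity correction has somewhat more power than Fisher (98.1% against 96.3% for the undiluted fallback).

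**6. Direction.** If the switch prevents nothing in placebo children (q = 0), they cause no loss. If it helps vigabatrin-arm children much more, the difference can grow. With e = 0.30, q = 0.2 in placebo and q = 0.8 in vigabatrin, the rates are 0.917 × 0.94 = 0.862 and 0.417 × 0.76 = 0.317. The difference is then 0.545 against 0.500 undiluted. With equal dilution the difference shrinks but the risk ratio does not change.

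**7. Event aligned with the trigger.** No child switched by a seizure then receives open-label drug before the event. If the plan's rates describe that event, power is as in step 2.

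**The case against.** The strongest reply is that the plan may already count both seizure types where it tests. The chi-square, Cox and Kaplan-Meier descriptions, and the sample-size text, do not restrict seizures to clinical ones. In the Vigabatrin and Placebo section, children who are seizure free at 24 months are those still on study drug. Since either seizure type takes a child off it, the term there implies neither type. On that reading the chi-square test already uses the aligned event. A reader might infer from the named endpoint that the plan counts an electrographic-only placebo child as a seizure-free success. The documents do not say so. What stands is that the tests leave the event undefined while the named hypothesis in the same paragraph says clinical.

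A reader might also infer that the comparison is certainly pulled to the null and that power is badly damaged. Neither is supported. Vigabatrin-arm children also switch, to a higher open-label target dose, so the direction is an expectation. At the planned rates power stays above 90% throughout the range. The 42% figure needs the fallback rate, a 30% share, a 79% open-label benefit and no benefit of the switch in the vigabatrin arm. The only nearby figure in the protocol, under 5% with unrecognised seizures at the first EEG, concerns another time point and does not fix the share.

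Finally, a clinical-seizure endpoint under intention to treat is legitimate and clinically direct. That supports keeping it as an analysis. It does not justify leaving the handling of switched children unstated.

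**Conclusion.** The mismatch between the named endpoint and the trigger for open-label drug is in the current text, and no rule resolves it. It should be corrected, but the defect is an undefined event rather than a demonstrated miscount. If only clinical seizures count, some loss of contrast is expected provided vigabatrin works. The loss is small at the planned rates. At the fallback rate it is enough to undo the claim of more than 90% power: at a 10% share when only placebo is diluted (88%), and by a 20% share when both arms are (85%). These sizes rest on an assumed electrographic-only share and an assumed open-label benefit. The Bayley-III comparison itself does not depend on how seizures are counted.

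**What to change.** Before unblinding, define the event for the chi-square, Kaplan-Meier and Cox analyses as the first clinical or centrally confirmed electrographic seizure, that is, the event that ends blinded treatment. Use the same definition for seizure freedom, and align the wording of secondary objective 1 and the Analyses section. Keep a clinical-only analysis as supportive, under intention to treat with follow-up continued through the switch. Report the number of electrographic-only first events by arm.

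The cost is endpoint and SAP wording. The EEGs are already collected and centrally read, and no visit or sample size changes. The small downside is that the event then includes EEG-only seizures, which are less directly clinical and are dated by visits 6 to 12 weeks apart.

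No change to clinical management is proposed. One passage does need reconciling. The protocol description ends blinded treatment at either seizure type, but its next sentence describes the blinded transition only for children with clinical seizures.
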